## **5.13 Lost to Follow-Up**

A participant will be considered lost to follow-up if he or she fails to return for 90 days scheduled visits and is unable to be contacted by the study team.

The following actions must be taken if the participant fails to return to clinic for a required study visit:

- The study team will attempt to contact the participant and reschedule the missed visit within 1-2 weeks and counsel the participant on the importance of maintaining the assigned visit schedule and ascertain if the participant wishes to and/or should continue in the study.
- Before a participant is deemed lost to follow-up, the investigator or designee will make every effort to regain contact with the participant (where possible, 3 telephone calls and, if necessary, a certified letter to the participant's last known mailing address). These contact attempts should be documented in the participant's medical record or study file.
- Should the participant continue to be unreachable, he or she will be considered to have withdrawn from the study with a primary reason of lost to follow-up.

## **6.0 RADIATION THERAPY DOSE/DELAYS MODIFICATIONS**

The planned course of radiation therapy is five fractions delivered every other day to each lesion. For plans unable to meet dose constraints to OARs, under coverage of the PTV in order to meet the constraints is recommended. Patients with delayed treatment starts of any duration may be treated using existing or new plans at physician discretion. Continuance of treatment for delays while on-treatment will be at the discretion of the treating physician.

## **7.0 REGULATORY AND REPORTING REQUIREMENTS**

The entities providing oversight of safety and compliance with the protocol require reporting as outlined below. Please refer to Appendix B for definitions and Appendix C for a grid of reporting timelines.

Adverse events will be tracked from start of treatment through 360 days following the completion of radiotherapy. All adverse events must be recorded on the toxicity tracking case report form (CRF) with the exception of:

- Baseline adverse events, which shall be recorded on the medical history CRF
- AEs that do not fall under the following categories
  - Gastrointestinal
  - Hepatobiliary
  - Immune system
  - Metabolic
  - Nervous system
  - Renal and urinary
  - Respiratory
  - Skin disorders
- AEs that are grade 1

Refer to the data submission schedule in Section 9.1 for instructions on the collection of AEs in the EDC.

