## PROTOCOL SUMMARY

Title:	A Trial of Palliative Lattice Stereotactic Body Radiotherapy (SBRT) for Patients with Sarcoma, Thoracic, Abdominal, and Pelvic Cancers
Study Description:	Lattice SBRT will be used to deliver palliative radiotherapy to large ( $\geq 4.5$ cm) tumors for patients with soft tissue sarcomas, thoracic cancers (including esophageal), abdominal, and pelvic cancers. The safety and efficacy of this approach will be assessed.
Objectives:	
Primary Objective:
 
 
1. To evaluate the efficacy and safety of 5-fraction palliative Lattice SBRT in patients with large lesions (<math>\geq 4.5</math> cm) who are planning to undergo palliative radiotherapy. This will be assessed with the co-primary endpoints of target lesion control at 6 months and rate of treatment-related severe toxicity within 6 months.
 
 
Secondary Objectives:
 
 
1. To assess the rate of treatment-related severe toxicity within 12 months of completion of treatment (i.e. late toxicity)
 
2. To assess patient reported toxicity with PRO-CTCAE
 
3. To assess patient-reported QoL with PROMIS
 
4. To assess patient-reported pain
 
 
Exploratory Objectives:
 
 
5. To evaluate blood for immune- and tumor damage-associated response with Lattice SBRT
 

Endpoints:	
Primary:
 
 
1. Rate of local control by RECIST at 6 months
 
2. Proportion of patients with treatment-related grade 3+ CTCAE v5.0 toxicity assessed within 6 months of completion of treatment
 
 
Secondary:
 
 
1. Proportion of patients with treatment-related grade 3+ CTCAE v5.0 toxicity at 12 months.
 
2. PRO-CTCAE assessment at baseline, post-treatment, 30 days, 3 months, 6 months, and 12 months.
 
3. PROMIS physical function, global health, anxiety, and depression assessment at baseline, post-treatment, 30 days, 3 months, 6 months, and 12 months.
 
4. Numeric Pain Scale at baseline, post-treatment, 30 days, 3 months, 6 months, and 12 months.
 
 
Exploratory: Peripheral blood immune-related biomarkers.

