## 2.0 OBJECTIVES AND ENDPOINTS

Objectives	Endpoints	Justification for Endpoints
Primary		
To evaluate the efficacy of 5-fraction palliative Lattice SBRT in patients with large lesions who are planning to undergo palliative radiotherapy ( $\geq 4.5$ cm).	Rate of target lesion local control at 6 months per RECIST 1.1	RECIST 1.1 is a standard measure of local control.
To evaluate the acute and sub-acute toxicity of 5-fraction palliative Lattice SBRT in patients with large lesions who are planning to undergo palliative radiotherapy ( $\geq 4.5$ cm).	Rate treatment-related, non-hematologic CTCAE v5.0 Grade $\geq 3$ toxicity at 6 months	SBRT to large tumors is traditionally associated with high dose to OARs, with sequelae of radiation-induced toxicities. As these patients have no effective treatment options, evaluation of the safety of this method of dose-

		escalation with SBRT is warranted. CTCAE v5.0 is a widely accepted standardized measure of treatment-related toxicity.
Secondary		
To assess pain response to Lattice SBRT	For patients that have pain, their pain level will be assessed with the pain Numeric Rating Scale (NRS)	The NRS is an 11-point scale for patient self-reporting of pain. This is selected because it is a reliable and clinically meaningful measure of pain that is extensively used in research and clinical practice.
To assess patient-reported toxicity outcomes	For patients that do not have pain, patient-reported symptom response will be assessed with PRO-CTCAE. A treatment site specific package of PRO-CTCAE measures will be defined for each treatment location (thorax, abdomen, pelvis, extremity)	PRO-CTCAE is a standardized inventory to collected patient reported symptomatic adverse events in clinical trials.
To assess patient reported quality of life outcomes	Patient reported quality of life and functional outcomes will be measured before treatment, after treatment, and at each follow up with the PROMIS Global, Physical Function, Pain Interference, Anxiety, and Depression system	This patient reported outcome inventory was selected because it is a reliable and clinically meaningful measure of patient reported toxicities and functional outcomes.
Exploratory		

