### **7.2 Exceptions to Expedited Reporting**

Events that do not require expedited reporting as described in Section 7.1 include:

- planned hospitalizations
- hospitalizations < 24 hours
- respite care
- events related to disease progression

Events that do not require expedited reporting must still be captured in the EDC.

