### 9.1 Adverse Event Collection in the Case Report Forms

All adverse events that occur beginning with start of treatment (minus exceptions defined in Section 7.0) must be captured in the Toxicity Form. Baseline AEs should be captured on the Medical History Form.

Participant death due to disease progression should be reported on the Toxicity Form as grade 5 disease progression. If death is due to an AE (e.g. cardiac disorders: cardiac arrest), report as a grade 5 event under that AE. Participant death must also be recorded on the Death Form.

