### 11.2 Study Endpoints

The co-primary endpoints are rate of local control of the treated (i.e. target) lesion at 6 months, and proportion of patients with treatment related grade 3+ CTCAE v5.0 toxicity. Local control will be determined by RECIST 1.1 analysis of baseline compared with imaging at 6 months. Imaging may include CT scan, PET/CT, or MRI. It is strongly suggested that the same imaging modality is used between baseline and at every follow-up timepoint for staging of disease.

Importantly, there are limited available data to determine expected local control of large tumors after SBRT. Almost all studies have focused on tumors with average maximal diameter of only 5.5 cm corresponding to a tumor volume of approximately 87 cc. In such studies, local control rates are approximately 70-85%. In the pilot study of Lattice SBRT at Washington University, the median treated tumor volume was 435 cc (N=14). Likewise, these few studies of SBRT for large tumors report a grade 3+ toxicity rate of 5-25%, varying based on tumor location.

Due to the lack of a reliable historical comparison, the enrollment target was defined by clinical considerations as opposed to power calculations for comparison with a historical control. This study instead seeks to establish the expected local control rate at 6 months for patients with such large tumors treated with Lattice SBRT. After discussing with internal and external stakeholders, we determined that a clinically reasonable bound on local control at 6 months would be 15%. Approximately 47 patients would be required to determine local control with a 95% confidence interval of +/- 15%; 67 patients will be enrolled to get 47 evaluable patients. We anticipate that up to 30% of patients may not be evaluable for local control at 6 months and are accounting for this potential drop-out rate by enrolling 67 patients. This is because patients with very large tumors needing palliative radiotherapy often have short survival.

Likewise, the study seeks to establish the expected grade 3+ treatment related toxicity rate for treatment of large tumors with lattice SBRT. The treatment will be considered safe if the grade 3+ treatment related toxicity rate is less than 20%, which is in line with prior studies of SBRT of large tumors.

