### **11.6 Continuous Toxicity Monitoring using Pocock-type boundary**

The toxicities will be reviewed and monitored on a continuous basis. Early stopping of this trial will be based on the excessive Lattice SBRT treatment emergent severe adverse events (TSAE) of grade 3 or higher non-hematological rate. We assume the TSAE rate is expected ~30% or less and a toxicity rate of 40% or more is not desired. Sequential boundaries will be used to monitor dose-limiting toxicity rate after three patients are enrolled and evaluable for toxicity. The accrual will be halted if excessive numbers of TSAE are seen, that is, if the number of TSAE is equal to or exceeds  $b_n$  out of  $n$  patients with full follow-up (see table below). This is a Pocock-type stopping boundary that yields the probability of crossing the boundary at most 0.3 when the rate of TSAE is equal to the acceptable rate of 0.3 (Ivanova, Qaqish, and Schell 2005).

number of patients	3	4	5	6	7	8	9	10	11	12	13	14	15	16	17	18	19	20	21	22
Boundary (bn)	3	3	4	4	5	5	6	6	7	7	7	8	9	9	9	9	9	10	10	
number of patients	23	24	25	26	27	28	29	30	31	32	33	34	35	36	37	38	39	40	41	42
Boundary (bn)	10	11	11	11	12	12	12	13	13	13	14	14	14	15	15	15	16	16	17	17
number of patients	43	44	45	46	47	48	49	50	51	52	53	54	55	56	57	58	59	60	61	62
Boundary (bn)	17	18	18	18	19	19	19	20	20	20	21	21	21	22	22	22	23	23	23	24
number of patients	63	64	65	66	67															
Boundary (bn)	24	24	25	25	25															

Thus, based on the continuous monitoring algorithm for toxicity using Pocock-type boundary, the study will halt if excessive Lattice SBRT -related adverse events occur in the 3 of the first 3 patients, or 4 of the first 6, or 5 of the first 9, or 5 of the 10 patients has completed the trial.

The operating characteristics including early stopping probability, expected number of TSAsEs and associated with the calculated boundaries are listed below.

TEAE rate	Early stopping (hitting the boundary) probability	Expected number of TEAEs	Standard deviation on number of TEAEs	Expected number of patients enrolled	Standard deviation of number of patients enrolled	Expected TEAE rate	Standard deviation on TEAE rate
0.30	0.3980	14.08	6.93	46.94	26.85	0.41	0.23
0.40	0.8648	9.76	7.27	24.38	22.99	0.56	0.22
0.50	0.9950	5.63	4.22	11.26	11.69	0.66	0.22
0.60	1.0000	3.85	2.24	6.41	5.76	0.75	0.21
0.70	1.0000	3.03	1.36	4.32	3.28	0.82	0.19
0.80	1.0000	2.56	0.88	3.20	1.98	0.89	0.15
0.90	1.0000	2.24	0.53	2.49	1.11	0.95	0.11

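### The adverse event recording rule in Section 7.0 leaves out organ classes that the co-primary grade 3+ toxicity endpoint and the stopping rule both count

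*Combined protocol and SAP*

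**What the plan says.** **Recording.** Section 7.0 requires adverse events on the toxicity case report form, with three separate exceptions: baseline events, grade 1 events, and "AEs that do not fall under the following categories". The classes listed are gastrointestinal, hepatobiliary, immune system, metabolic, nervous system, renal and urinary, respiratory, and skin. Section 9.1 repeats the rule: "All adverse events that occur beginning with start of treatment (minus exceptions defined in Section 7.0) must be captured in the Toxicity Form". In the Section 9.0 schedule, the Toxicity Form is the only form dedicated to toxicity.

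**Endpoint.** The Protocol Summary defines the second primary endpoint as "Proportion of patients with treatment-related grade 3+ CTCAE v5.0 toxicity assessed within 6 months of completion of treatment". Section 2.0 has "Rate treatment-related, non-hematologic CTCAE v5.0 Grade" 3 or higher, so its only restriction by type of event is the hematologic one. Section 11.2 sets the criterion: "The treatment will be considered safe if the grade 3+ treatment related toxicity rate is less than 20" per cent.

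**Stopping rule.** Section 11.6 monitors "treatment emergent severe adverse events (TSAE) of grade 3 or higher non-hematological rate". Again only hematologic events are left out.

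**Text that limits the gap.** Section 9.1 brings back deaths: "If death is due to an AE (e.g. cardiac disorders: cardiac arrest), report as a grade 5 event under that AE". Section 7.2 adds: "Events that do not require expedited reporting must still be captured in the EDC". The Schedule of Activities provides for adverse event review at visits, and Section 9.0 lists a Follow Up Form whose contents are not described. The oversight reporting in Section 10.0 and Appendix C has no class filter.

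**The concern.** What must be recorded is narrower than what must be counted. Grade 1 has its own bullet in Section 7.0, so the class exemption is not confined to mild events. Nothing confines it to unrelated events either.

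The protocol itself treats some exempt sites as relevant. Section 5.5.2.3 sets dose constraints for heart/pericardium, great vessels and femoral heads, yet no cardiac, vascular or musculoskeletal class is on the list. Appendix D asks pelvic patients about vaginal and sexual symptoms, yet no reproductive class is listed.

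At stake is a co-primary endpoint and the safety statement drawn from it. A missing event can lower the observed rate but never raise it. Grade and attribution that were not collected at the time may be hard to recover, and no analysis method restores an event that was never recorded.

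**Working it through.** **1. Which events fall in the gap.** This reads the categories in Section 7.0 as organ classes.

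| Event | Counts toward the endpoint (2.0, 11.2) | Required on the Toxicity Form (7.0, 9.1) |
|---|---|---|
| Related grade 3–4, one of the eight classes | Yes | Yes |
| Related grade 3–4, e.g. cardiac, vascular, musculoskeletal, reproductive | Yes | No |
| Related grade 5, any class | Yes | Yes, through the rule on deaths in 9.1 |

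The gap is therefore non-fatal grade 3–4 events outside the eight classes. A patient is lost from the count only if every qualifying event that patient has is of this kind.

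**2. Effect on the under-20% criterion.** The plan gives no figure to reproduce and no share of grade 3+ events outside the eight classes, so the unrecorded shares below are assumptions for illustration.

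Inputs and assumptions:
- n = 67 treated patients, all evaluable for toxicity. The enrolment figure is from Section 11.2.
- The criterion is read as a point estimate. Since 13/67 = 19.4% and 14/67 = 20.9%, safe means a recorded count X of at most 13.
- p is the true patient-level rate and f the share of affected patients unrecorded, so X ~ Binomial(67, p(1 − f)).

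P(X ≤ 13):

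| True rate p | f = 0 | f = 10% | f = 20% |
|---|---|---|---|
| 10% | 0.994 | 0.998 | 0.999 |
| 15% | 0.879 | 0.938 | 0.974 |
| 20% | 0.524 | 0.686 | 0.825 |
| 25% | 0.181 | 0.330 | 0.524 |

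For example, p = 25% with f = 20% gives a recorded rate of 0.25 × 0.80 = 0.20, hence the same 0.524 as a fully recorded 20%.

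**3. A check that assumes no share.** If the true count is 14 of 67, one unrecorded patient turns 20.9% into 19.4% and reverses the verdict. A true count of exactly 14 has probability 0.117 at p = 20% and 0.087 at p = 25%.

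**4. Stopping rule, only if it too is counted from the form.** I ran an exact recursion over the printed boundary from n = 3 to 67. The first boundary row, as extracted, has 19 values for 20 positions. I repeated one value at each possible position and report the range. The true rate is the 40% that Section 11.6 calls undesired.

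| Unrecorded share | Recorded rate | Probability of crossing |
|---|---|---|
| 0 | 0.40 | 0.848–0.862 (plan's table: 0.8648) |
| 10% | 0.36 | 0.670–0.698 |
| 20% | 0.32 | 0.447–0.490 |

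**The case against.** The strongest reply is that the harm is conditional. No section names the data source for the endpoint, so counting from the Toxicity Form is an inference, although the natural one given Section 9.0. This stands, and the bias is stated conditionally here.

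Second, Section 7.2 can be read broadly: any event not needing expedited reporting goes into the EDC, and Section 7.0 points to 9.1 for EDC collection. The cardiac example for deaths in 9.1 also suggests drafting that was not reconciled rather than a deliberate choice. But Section 7.2 names no form and does not override 7.0, and it may cover only the events it lists. Section 9.1, to which 7.0 points, restates the exemption. The texts are in tension, and the tension does not settle the matter in favour of recording.

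Third, Sections 10.0 and 11.6 describe continuous monitoring without a class filter, so the stopping count may be complete. The stopping figures also use a 40% rate, above the 5–25% that Section 11.2 reports from earlier studies. Both points stand, and the stopping effect is secondary.

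Fourth, most tissues in the Section 5.5.2.3 table fall inside the eight classes, so the unrecorded share may be small, and nothing in the documents supports 10% or 20%. That is fair, although tissue counts are not event rates. Appendix D is also weak support, because it concerns patient-reported items for a secondary endpoint.

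Finally, the co-primary endpoint needs only related events, so recording unrelated ones goes further than it requires. The reason for doing so is that Section 11.6 refers both to treatment-emergent and to Lattice SBRT-related events.

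**Conclusion.** The concern holds. Followed as written, Sections 7.0 and 9.1 allow qualifying non-fatal grade 3–4 events to be left off the only dedicated toxicity form, while the endpoint and the stopping rule would count them. The mismatch rests on the text alone and is firm, given the organ-class reading.

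The resulting bias depends on two conditions: that staff record no more than is required, and that the endpoint is counted from the Toxicity Form. Under those conditions its direction is certain, toward declaring the treatment safe. Its size is not estimable from the documents. The illustration shows little effect in the lower part of the 5–25% range in Section 11.2 and a material one near the 20% limit. This must be fixed, because it affects data capture for a co-primary endpoint.

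**What to change.** - In Section 7.0, and by reference in 9.1, limit the organ-class exemption to grade 2 events. Every post-baseline grade 3+ event in any class that the endpoint or stopping rule covers, related or not, then goes on the Toxicity Form with attribution, through 360 days.
- Settle the hematologic scope at the same time: Sections 2.0 and 11.6 exclude hematologic events, while the Protocol Summary and Section 11.2 do not.
- In Section 7.2, name the form on which events are captured.
- In Sections 11.2 and 11.6, state that the counts are taken from the Toxicity Form.
- If an endpoint limited to the eight classes is what the sponsor intends, say so in Sections 2.0, 11.2 and 11.6. That would narrow the safety claim.

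The cost is extra form entries with attribution for grade 3+ events in the classes now exempt (a number the documents do not allow us to estimate) and wording changes in the sections named. The reported toxicity rate may be less favourable.

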### **7.1 WU PI Reporting Requirements**

#### **7.1.1 Reporting to the Human Research Protection Office (HRPO) at Washington University**

Reporting will be conducted in accordance with Washington University IRB Policies.

Pre-approval of all protocol exceptions must be obtained prior to implementing the change.

### **7.1.2 Reporting to the Quality Assurance and Safety Monitoring Committee (QASMC) at Washington University**

The PI is required to notify the QASMC of any unanticipated problems involving risks to participants or others occurring at WU or any BJH or SLCH institution that has been reported to and acknowledged by HRPO. (Unanticipated problems reported to HRPO and withdrawn during the review process need not be reported to QASMC.)

QASMC must be notified within **10 days** of receipt of IRB acknowledgment via email to [[contact]](mailto:[contact]). Submission to QASMC must include the myIRB form and any supporting documentation sent with the form.

### **7.2 Exceptions to Expedited Reporting**

Events that do not require expedited reporting as described in Section 7.1 include:

- planned hospitalizations
- hospitalizations < 24 hours
- respite care
- events related to disease progression

Events that do not require expedited reporting must still be captured in the EDC.

## **8.0 CORRELATIVE STUDIES**

### **8.1 Blood Sample Collection and Processing**

Patients will have up to 30 mL of anticoagulated blood collected in up to 3 EDTA purple top tubes at the following time points:

- Baseline
- immediately after radiotherapy completion (Fraction 5)
- 14 days after radiotherapy
- 30-days follow-up

All samples will be marked with the patient's study number, initials, and date of sampling with the use of an indelible marker.

Blood and tissue samples will be stored in [name] lab in the Cancer Biology Division of the Department of Radiation Oncology.

#### **8.1.1 Plasma and Whole Blood**

Each sample will be labeled with a unique de-identified specimen ID number, and stored in [name] lab until analysis. Specifically, blood samples (up to 30 mL) will be collected in 3 EDTA (10 mL each) purple top tubes at baseline, post-

treatment (i.e. immediately following fraction 5), 14 days after treatment, and at 30 days follow-up. EDTA whole blood samples will be spun at 1200 g and processed for platelet depleted plasma and peripheral white blood cells. Nucleated white blood cells will be isolated using Ficoll or Lymphoprep extraction using Sepmate tubes, washed in phosphate buffered saline, then divided into approximately 10 x 10^6 cells/aliquot, and cryopreserved at -80° C for 24-72 hours, then moved for longer term storage in a LN2 tank. All plasma and aliquots of platelet-depleted whole blood will also be stored at -80° C.

All samples should be sent to:

[name]., Ph.D.  
[name]. (Lab Manager)  
[name]  
[contact], [contact] (cell)

